Assessment of the injury in the hyper acute phase is challenging, the ankle is often so swollen and painful that it cannot easily be touched. Most patients are advised to rest, elevate, apply ice and compression, and are often issued with crutches. Use of X-ray has been effectively controlled through the Ottawa guidance,⁶ with only the most concerning injuries being X-rayed (or equivalent) to exclude fracture. Where clinicians are concerned about the degree of injury, most providers operate a system of review within one week in a trauma or equivalent injury service. This time frame allows dissolution of some swelling, and greater certainty in ascertainment of injury severity and presence of other significant mechanical derangement.⁷ Treatment options at this stage include further watchful waiting, diagnostics, intensive physiotherapy or immobilisation. Surgery may be considered at this stage, although most centres would initiate a test of conservative treatment first. We have previously published a survey of practice, which whilst quite an old publication remains an accurate reflection of the current management.⁸

Value of a prognostic tool

A prognostic tool is indicated to identify patients likely to experience poor outcome. There are effective treatments available, and it is generally accepted that early intervention is preferable. There are clearly several steps where better prognostic information could yield benefit to the NHS and to patients as follows; [1] Increase the certainty that an early review is merited, and avoid unnecessary appointments [2] Better target treatments and diagnostics, earlier in the recovery pathway [3] Be re-assured that patients not followed up are on a positive recovery trajectory. Volume is a key issue for sprains. Cost savings will accrue if treatments are more efficiently targeted.

Any prognostic tool needs to be simple to complete in the ED. Ideally a tool which requires a once only administration is preferable, although there are several possibilities which we can explore in the CAST data set. The issues that we will explore during development will be variable selection, timing and method (self-report versus clinical examination).

Requirements of a prognostic tool

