The participants will be a maximum of 12 clinicians (including ED doctors, trauma/sports physicians, physiotherapists, ED nurses, and minor injury unit staff), and 12 patients (representing a range of age, gender and physical activity/sport participation). The tool will then undergo final revision and common sense testing before release for external validation. Our plan will be to present two schedules of data collection for completion (excluding data on sample characteristics that are not contained in either schedule). The first will be prognostic tool as generated by the development data set. These will require a degree of formatting to convert data collected in a clinical research form, to an easy to complete prognostic tool. The additional predictive factors will also be formatted in a similar and completely complementary manner, but collected on the separate schedule (and after completion of the primary tool). The two schedules will be collected by the same clinician. In this way if any of the additional factors is confirmed as important, we will add them into the final tool, causing least disruption to the process of validation. If there is more than one additional predictive factor, we will randomise the order of data presentation across participants to gain insight into whether the order or opportunity to provide additional data in anyway biases the sample.

All participants of the consensus exercise will provide consent to participate. PPI members will be paid for their time and contribution, clinicians will not.

Stage 3: Externally validate and optimise the tool in a new cohort of patients recruited from NHS Emergency Departments

We will externally validate the prognostic tool developed in stages 1 and 2 in a new prospective cohort. We will recruit 675 people from 5 EDs, from a pool of 7,500 to 10,000 ankle sprains per annum at a conservative rate of 15 sprains per centre per month. We have provisional agreement from an additional 5 EDs to participate if required.

We cannot be completely certain of how this element of the study will run, as this will vary depending on the final tool. We have at this stage assumed that the tool will require contact at initial attendance and one early follow up visit (at around 5 days), and will include a mix of self-report and clinical tests. We have considered a range of other possibilities, and can provide these if needed.

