Whilst we expect challenges, we do not anticipate any substantial difficulty with approach and recruitment.

Selection criteria:

Inclusion: Adults (>16 years of age) with an acute ankle sprain (<7 days old) who provide informed consent to participate. There will be no upper age limit.

Exclusions: Ankle fracture (excluding flake fracture < 2mm); Other recent (<3 months) lower limb fracture.

Procedure: ED staff will be asked to approach potential participants, provide a brief explanation of the study, administer the prognostic tool and record their clinical exam on a standard form. A standard approach will be instituted across all A&E departments based on our experience of running previous trials. We anticipate that completion of the tool will fall into the scope of any practitioner who is capable of taking a history and performing a simple ankle examination. In standard practice this would be nursing, medical, surgical or physiotherapy staff with experience or training in basic orthopaedic and injury management. We will develop a short pro-forma that serves two purposes (1) collection of routine core clinical data set in a tick box format and (2) A tick box to ensure that clinicians have provided potential participants with the trial information pack and a brief explanation of the trial. One copy of the form will be filed to the medical notes as a treatment record and a second copy is passed to the research team (with the patients consent) to notify them that a patient has been asked to participate in the trial. Provided that the clinical centres are involved in the development of the pro-forma, we have found this system to work well and once embedded in the system, to act as a reminder to invite patients into the trial. The form also enables us to check ED attendance statistics against the number of people being approached.

Formal consent to participate in the research will be taken by CLRN staff/the research team either by post or by telephone within one week. Participants will be consenting to allow us to use the data collected in the ED attendance (prognostic tool +/- any additional variables), and follow up questionnaires at 4 and 9 months so we can map the recovery trajectory and final recovery status at 9 months. A questionnaire at 4 months will also serve as reminder of the study, and as loss to follow up is likely to become larger over time, will ensure that we have responses on as many participants as possible.

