All aspects of the project will comply with Good Clinical Practice and the Declaration of Helsinki. All participants will be asked for written informed consent. Although some of the research is based in the Emergency Department with the attendant problems of that, the people we will approach will not fulfil the criteria of incapacity under the Mental Capacity Act (2005). NHS research ethics committees have previously approved a variety of telephone and postal consent methods recognising that this is an acute injury, that the ability to give a minimum of 24 hours between initial approach and consent may be compromised.

There are no ethical issues around collecting risk information without sharing this with clinicians or patients in the validation study. The rationale is that the prognostic tool is experimental until the end of the validation period. We do not know whether it enhances or detracts from routine clinical care. We will be very clear to ensure that all participating clinicians and patients are aware of this. We will not be withholding any form of standard practice. Neither do we shield the clinician from the responses made, only from the overall prediction score and interpretation. We will not calculate the overall prediction score until the end of the follow up period.

Risks and benefits:

The risks to participants are very small. This is an observational study, although we will be “intervening” with a prognostic tool. It is possible that the tool may include a performance test which if inappropriately implemented might cause prolongation or exacerbation of symptoms, or re-injury. We will act to minimise the risks of testing through careful selection of test items and training.

Data retention

Clinical Research Forms will be securely stored for 15 years after completion of the study. Electronic copies of the study data set will be retained indefinitely, and after a period of 3 years will be made available to other investigators on request and subject to a data sharing agreement. Oxford Clinical Trials Research Unit (OCTRU) has Standard Operating Procedures to ensure adherence with the Data Protection Act (2003), ICH and MRC good clinical practice guidelines.

Monitoring and safety reporting

The trial will have a Trial Steering Committee (comprising 3 independent members and 2 dependent members ([name] and [name])). We will not formally constitute a separate Data Monitoring and

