Ethics Committee as this is not a comparative interventional trial. The three independent committee members will review safety, recruitment and ethical data, and would be able to close the trial.

We will use a risk adapted approach to monitoring. Recruitment and progress against milestones will be monitored by the study team at monthly Trial Management Meetings. A quality assurance programme will ensure consistent and high quality approaches to consent and implementation of the clinical rule. We will define an adverse event as one that occurs directly as a result of the clinical prediction tool (patient report of substantial worsening of pain and/or symptoms within 2 days of the test) and serious adverse events as any hospitalisation or death that occurs within 2 days of the test, and would not have been anticipated as part of clinical management at initial presentation.

Inclusion of people from ethnic minorities

Our sampling frame of EDs include a number of departments that have catchments with substantial ethnic minority communities (in particular Birmingham Heartlands). In the HTA funded Managing Injuries of the Neck Trial, we translated materials into a range of languages but found no evidence that the translated materials were used in preference to an English language version. We will explore the need to translate materials at each site, as well as the range of languages and take appropriate action. Translation services are available in NHS Trusts.

3. Research Governance

The research will be sponsored by the University of Oxford (with appropriate insurance policies in place) and follow Oxford Clinical Trial Research Units Standard Operating Procedures. This study will be fully compliant with the research governance framework and MRC Good Clinical Practice guidelines.

4. Study Management

This study will require careful management with stages 1 and 2 feeding vital information into stage 3. The Principal Investigator will be [name]. Day-to-day management will be undertaken by [name] and an experienced Study Co-ordinator. Study management group meetings will be held on a monthly basis to monitor progress and obtain input from the appropriate co-applicants and site investigators at the relevant stages of the study. In addition, 6-monthly co-applicant meetings will be held to ensure close involvement from all parties.

5. Project Timetables and Milestones

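### The serious-event rule dates the admission or death rather than the harm behind it, so a tool-related adverse event stays non-serious if the admission or death it causes comes on day 3 or later

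*Protocol*

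**What the plan says.** All the relevant wording is in section 2 of the protocol (Ethical considerations for all stages of the project).

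- **Adverse event** (Monitoring and safety reporting): an event caused directly by the prediction tool, explained in brackets as "patient report of substantial worsening of pain and/or symptoms within 2 days of the test".
- **Serious adverse event** (same paragraph): "serious adverse events as any hospitalisation or death that occurs within 2 days of the test", with a second condition that the event "would not have been anticipated as part of clinical management at initial presentation".
- **Source of harm** (Risks and benefits): "It is possible that the tool may include a performance test which if inappropriately implemented might cause prolongation or exacerbation of symptoms, or re-injury".
- **Oversight** (Monitoring and safety reporting): there is no separate data monitoring committee. "The three independent committee members will review safety, recruitment and ethical data, and would be able to close the trial".

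Stage 3 leaves the content of the tool open: "We cannot be completely certain of how this element of the study will run, as this will vary depending on the final tool". It also plans "follow up questionnaires at 4 and 9 months so we can map the recovery trajectory and final recovery status at 9 months", and those questionnaires include health service resource use.

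**The concern.** Both definitions use a 2-day window, but the windows attach to different things. For an adverse event the window covers the worsening. For a serious event it covers the hospitalisation or death. Harm from a test and the admission it causes need not fall in the same two days. When they do not, the stated rule labels as non-serious an event that the tool caused and that put the participant in hospital.

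What is at stake is the label under which the event reaches the independent members, and the serious-event count that is finally reported for the tool. The protocol plans to make a suitable tool freely available on the web (section 8), so its safety record will be read outside this cohort.

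**Working it through.** The protocol gives no figure on this point to reproduce. The check applies the two definitions to each possible timing, with the test on day 0.

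| Worsening caused by the tool | Unanticipated admission or death | Adverse event? | Serious adverse event? |
|---|---|---|---|
| day 0–2 | none | yes | no |
| day 0–2 | day 0–2 | yes | yes |
| none reported | day 0–2 | no | yes |
| day 0–2 | day 3 or later, resulting from the worsening | yes | **no** |

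The fourth row is the gap. The third row shows why the 2-day clause should stay. The serious-event definition does not itself require causation by the tool, so the window is its only link to the test, and it catches unanticipated admissions in which no worsening was reported.

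Three other parts of the protocol might have closed the gap:

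1. *The condition that the event was not anticipated.* It is joined to the window by "and" in substance: both conditions must hold. It narrows the definition and does not lengthen the window.
2. *The commitments to Good Clinical Practice and to the trial unit's operating procedures* (sections 2 and 3). They are general. They state no other definition of a serious event and no rule for following an adverse event to its outcome.
3. *The resource-use items at 4 and 9 months* (Stage 3, Procedure). They could reveal a later admission, but nothing links them to classification as serious.

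**Effect of one case.** The inputs are the target of 675 participants (Stage 3, Sampling) and, as an illustrative assumption, no other serious event and full ascertainment. With exact one-sided 95% upper limits:

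- As the rule stands, 0/675: upper limit 1 − 0.05^(1/675) = 0.443%.
- With the event upgraded, 1/675 = 0.148%: upper limit is the 0.95 quantile of a beta(2, 674) distribution = 0.701%.

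**Effect on the main results.** The sample size rests on 100 outcome events: 675 × 0.75 retained × 0.20 event rate = 101. No safety quantity enters that calculation, or the planned calibration, discrimination and net-benefit analyses.

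**The case against.** The best defence is that the window is a deliberate and proportionate choice. The study is observational, the protocol calls the risks very small, test items are to be selected and staff trained to limit harm, and monitoring is stated to be risk-adapted. People with ankle sprains have recurrent sprains and persistent pain anyway, and a short window keeps ordinary later ankle care out of the serious-event count. That justifies keeping the window. It does not justify ignoring the outcome of an event already recorded as caused by the tool, which is a much smaller group than all later admissions.

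A second defence is that nothing is hidden: the event is recorded as an adverse event, the independent members review safety data in general, and no closure rule depends on a serious-event count. This stands, and it limits the consequence to a label and a count. A reader might infer that the committee would be unaware of the harm; the documents do not support that.

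A reader might also infer from the account of usual care that operations after a test-related re-injury would typically fall outside the window, since it says "Surgery may be considered at this stage, although most centres would initiate a test of conservative treatment first". That does not follow. The sentence concerns surgery for the original sprain, and the review it refers to is part of the pathway after attendance, whereas the safety window runs from the test. Stage 3 assumes a possible visit at around 5 days. A test done then has a window running to about day 7 after attendance, which could include a review held within one week. The documents do not show how often a resulting admission would fall late.

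Finally, the unit's operating procedures are not shown and may require follow-up of adverse events. They may, but the protocol's explicit definition would still govern what is called serious. The protocol is marked as a pre-ethics draft, so the wording can be corrected before use.

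**Conclusion.** The point holds as a minor defect of definition. By the stated rule, an adverse event caused by the tool is non-serious if the unanticipated admission or death it leads to falls on day 3 or later.

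This rests on the literal wording and on there being something in the tool that can cause harm. The protocol treats a performance test as possible, not settled. The sequence is likely to be rare and may never occur. No rate of test-related harm or admission is given, so no expected number of mislabelled events can be stated. The change from 0/675 to 1/675 shows what one case would do and is not a forecast. No estimate, sample size or validation result is affected. It is worth considering because it is cheap to correct.

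**What to change.** Keep the existing clause on unanticipated hospitalisation or death within 2 days of the test, and add after it:

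*An adverse event with onset within 2 days of the test is upgraded to serious if it is judged to have led to a later hospitalisation or death not anticipated at initial presentation.*

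State that upgrades are reported to the independent committee members when the site or study team learns of them. Use the 4- and 9-month resource-use items only as a back-up check, and only for participants with a recorded adverse event. They cannot be the main route: recruitment is planned for 10 months, so much of that information would come too late for the committee to act on, and the protocol allows for 25% loss to follow-up.

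The cost is one sentence and a check of data already planned, with no new visit or form. The real downside is a relatedness judgement for a few events, without a comparison group and made harder because recurrent sprain is itself part of the outcome being predicted. If the final tool contains nothing that could cause harm, the sentence will simply not be used.

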Stage 3: Our experience has shown the value of early PPI input into the design of patient-facing materials to ensure they are understandable and address issues of relevance to ED patients. We will seek input on study procedures to ensure that burdens placed on participants are justifiable and well explained, also to identify potential recruitment barriers.

Reporting & dissemination: We will collaborate with our reps when writing the funders' report, subsequent publications and developing a strategy for dissemination to users. Attendance at conferences by PPI reps will be supported (e.g. INVOLVE conference). Training needs for reps will be addressed on an individual basis. Management: PPI reps will be invited to attend 6 monthly collaborator meetings. A PPI rep will be appointed to the Independent Steering Committee.

8. Dissemination and projected outputs

We will publish an HTA monograph of the project. Currently no systematic review has been published specifically investigating prognostic factors for poor recovery following acute ankle sprain. We will publish a systematic review of prognostic factors in a peer-reviewed journal. We anticipate also publishing the results of the modified nominal group element of the study, which is likely to also yield new perspectives on the future research agenda for ankle sprain. Following analysis of the internal and external validation of the tool, we will publish the findings in a peer-reviewed journal and disseminate through international conferences. Any publications will adhere to the PRISMA (for systematic review)⁴³ and STROBE guidelines⁴⁴. We also plan to disseminate to patient and public groups e.g. INVOLVE conference. More recently our research group has been looking to social media to promulgate research findings. We are establishing a monthly Blog and Twitter and will utilise these media to increase visibility of the research findings. Our group is working alongside the Oxford CLARHC, so we would hope to utilise this infra-structure to study and promote implementation. Should we develop a suitable tool, we will make the tool freely available on the web, with a simple registration to track areas and level of impact. We will investigate the possibility of using a mobile app for scoring the tool and utilising existing infrastructure used by clinicians to access decision tools e.g. MDCalc.com

9. Flow diagram

10. Appendices

Appendix 1 - List of variables available from CAST dataset related to clinical and empirical importance

	Available in CAST data set	Not available in CAST data set
Clinically important	Grade of sprain Weight Bearing ability Pain intensity Swelling (S-R) Initial Ligament testing Recurrent sprains Reduced Range of Motion (S-R) Type of employment Type of recreational activities Frequency of sports participation	Reduced Range of Motion (C-R) Location of injury Syndesmosis test positive
Moderate to strong relationship with outcome (function unless specified)	Previous sprain (outcome pain/symptoms) ¹ Males ¹ C-R severity ² Palpation score ² Function score ² Pain ² Swelling ² Ankle Function Score ^{2,3} ED attendance (outcome instability) ³ S-R activity limitation ⁴ Age ^{5,6} Weight-bearing status ⁵ Injury mechanism ⁵ Females ⁶	High level athlete ¹ Syndesmosis sprain ⁷
Items confirmed in prognostic tool	None	None
Abbreviations	S-R = Self-Reported C-R = Clinician-Reported	
References	1. Linde (1986), 2. de Bie (1997), 3. van Middelkoop (2012), 4. Wilson and Gansneder (2000), 5. O'Connor et al (2013), 6. Akacha and Hutton (2011), 7. Gerber et al (1998)	

